Informal care includes different types of unpaid support which serve to compensate for the inability of subjects, usually provided by relatives or friends. This information is obtained from questionnaires applied directly to caregivers in which time spent on helping the elderly in basic Activities of Daily Living and Instrumental Activities will be specified. The time spent on these activities will be evaluated in monetary terms using 'proxy goodmethod "or" replacement method "which assesses the time spent on informal care adjusted to market prices of a professional who has to do this work (social service Careful formal).

The economic evaluation will be developed to take into account several aspects: financing health care (including only direct health costs), finance formal care (including the direct costs of health and social services) and social perspective (including all relevant costs: direct medical care + formal care (social services) and informal care.

Outcome measures:

Cost-effectiveness analysis

The cost-effectiveness analysis (CEA) is the most common test used in health economics to decide between different treatments for the same condition. In a CEA, the costs are measured in monetary units, while the benefits are measured as outcomes or in natural units. "Incremental cost-effectiveness ratio" (ICER) is estimated to show a difference in health outcomes per unit cost, after a follow-up period between intervention and usual care. The incremental cost-effectiveness is expressed by the following relation:

$$ICER = \frac{C_a - C_b}{B_a - B_b}$$

Where Ca is the cost of the intervention group and Cb is the cost of the usual care group. Ba will be health benefits in the intervention group and Bb health benefits in the usual care group, both measured in terms of change of the clinical results of the baseline.

In this study the primary outcomes will be the difference in functional status after the intervention compared with usual care group. This study will assess the cost-effectiveness of the intervention of a geriatrician compared with usual care from the perspective of society and the health care system.

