Feeding 0 = unable 5 = needs help cutting, spreading butter, etc., or requires modified diet 10 = independent	0  5  10 
Bathing 0 = dependent 5 = independent (or in shower)	0  5 
Grooming 0 = needs to help with personal care 5 = independent face/hair/teeth/shaving (implements provided)	0  5 
Dressing 0 = dependent 5 = needs help but can do about half unaided 10 = independent (including buttons, zips, laces)	0  5  10 
Bowels 0 = incontinent (or needs to be given enemas) 5 = occasional accident 10 = continent	0  5  10 
Bladder 0 = incontinent, or catheterized and unable to manage alone 5 = occasional accident 10 = continent	0  5  10 
Toilet Use 0 = dependent 5 = needs help, but can do something alone 10 = independent (on and off, dressing, wiping)	0  5  10 
Transfers (bed to chair and back) 0 = unable, no sitting balance 5 = major help (one/two people, physical), can sit 10 = minor help (verbal or physical) 15 = independent	0  5  10  15 
Mobility (on level surfaces) 0 = immobile or < 50 yards 5 = wheelchair independent (inc. corners) > 50 yds 10 = walks with help of one person (verbal or physical) > 50 yards 15 = independent (but may use any aid; for example, stick) > 50 yards	0  5  10  15 
Stairs 0 = unable 5 = needs help (verbal, physical, carrying aid) 10 = independent	0  5  10 
TOTAL (0-100)	

THE LAWTON INSTRUMENTAL ACTIVITIES OF DAILY LIVING SCALE

A. Ability to Use Telephone

1. Operates telephone on own initiative; looks up and dials numbers.....	1
2. Dials a few well-known numbers.....	1
3. Answers telephone, but does not dial.....	1
4. Does not use telephone at all.....	0

B. Shopping

1. Takes care of all shopping needs independently	1
2. Shops independently for small purchases.....	0
3. Needs to be accompanied on any shopping trip	0

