4. Completely unable to shop	0

C. Food Preparation

1. Plans, prepares, and serves adequate meals independently	1
2. Prepares adequate meals if supplied with ingredients.....	0
3. Heats and serves prepared meals or prepares meals but does not maintain adequate diet.....	0
4. Needs to have meals prepared and served.....	0

D. Housekeeping

1. Maintains house alone with occasion assistance (heavy work).....	1
2. Performs light daily tasks such as dishwashing, bed making.....	1
3. Performs light daily tasks, but cannot maintain acceptable level of cleanliness	1
4. Needs help with all home maintenance tasks.....	1
5. Does not participate in any housekeeping tasks.....	0

E. Laundry

1. Does personal laundry completely	1
2. Launders small items, rinses socks, stockings, etc.....	1
3. All laundry must be done by others	0

F. Mode of Transportation

1. Travels independently on public transportation or drives own car.....	1
2. Arranges own travel via taxi, but does not otherwise use public transportation	1
3. Travels on public transportation when assisted or accompanied by another	1
4. Travel limited to taxi or automobile with assistance of another.....	0
5. Does not travel at all.....	0

G. Responsibility for Own Medications

1. Is responsible for taking medication in correct dosages at correct time	1
2. Takes responsibility if medication is prepared in advance in separate dosages	0
3. Is not capable of dispensing own medication	0

H. Ability to Handle Finances

1. Manages financial matters independently (budgets, writes checks, pays rent and bills, goes to bank); collects and keeps track of income.....	1
2. Manages day-to-day purchases, but needs help with banking, major purchases, etc	1
3. Incapable of handling money	0

GERIATRIC DEPRESSION SCALE (GDS)

Choose the best answer for how you have felt over the past week:

1. Are you basically satisfied with your life?

YES / NO

2. Have you dropped many of your activities and interests?

YES / NO

3. Do you feel that your life is empty?

YES / NO

4. Do you often get bored?

YES / NO

5. Are you in good spirits most of the time?

YES / NO

6. Are you afraid that something bad is going to happen to you?

YES / NO

7. Do you feel happy most of the time?

YES / NO

8. Do you often feel helpless?

YES / NO

9. Do you prefer to stay at home, rather than going out and doing new things?

YES / NO

10. Do you feel you have more problems with memory than most?

YES / NO

11. Do you think it is wonderful to be alive now?

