4. WHAT IS YOUR MAIN WORKING SITUATION?

- I am employed

- I am unemployed
- Retired or pensioner ⇒ Skip to question #7
- Domestic tasks ⇒ Skip to question #8
- N/A ⇒ Skip to question #8

5. Have you had any work-related problem for caring the subject in the last 3 months?

- Yes
- No ⇒ Skip to question #8

6. In case of yes, please specify this

- I requested ___ days leave of absence
- I was working ___ hours less a day for ___ days
- I am working ___ hours less a day
- I do not work less hours a day but I have problems fulfilling my working hours
- I had to leave work because of illness the person I care
- Other problems: _____

7. Retirement (only to be answered in case the carer is retired or a pensioner)

c. Have you had to retire early to care for the subject?

- Yes
- No ⇒ Skip to question #8

d. In case of yes, please specify:

- I retired early at the age of ___ years

SOCIAL, FAMILY AND LEISURE TIME- RELATED PROBLEMS

8. Have you had any family, social o leisure time-related problem for caring the subject in the last 3 months?

Yes No ⇒ Skip to question #10

9. In case of YES, please specify this(multiple choice option)::

- I had to reduce my leisure time
- I have conflicts with my partner or my family
- I have no time to see or visit my friends
- I have no time to take care of myself or other people
- I have failed to start a family / I have not been able to have children (or more children)

Regarding the role played by you as PRINCIPAL CARER...

10. How much time do you invest in a normal DAY for each one of the activities?

Please specify the approximate time you spend daily on each activity

On basic hygiene and dressing or changing them	hours	minutes	a day
On bathing or showering them	hours	minutes	a day
On feeding them	hours	minutes	a day
On helping them to move around within the house	hours	minutes	a day
On cooking and preparing meals	hours	minutes	a day

Administration of drugs	hours	minutes	a day
-------------------------	-------	-------	-------	---------	-------

11. How much time do you invest in a normal WEEK on each one of the following activities?

Please specify the approximate time you spend weekly on each activity

On helping them to travel outside the house	hours	minutes	a week
On helping them to contact health care suppliers	hours	minutes	a week
On helping them to organise home adaptations	hours	minutes	a week
On shopping	hours	minutes	a week
On financial, administrative or legal affairs	hours	minutes	a week

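### The carer time tables have no row for housework or laundry, so informal care cost is understated unless carers log that time elsewhere, and the social-perspective cost difference can be misstated

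*Combined protocol and SAP*

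**What the plan says.** Section 10 (informal care) says that carers complete questionnaires in which "time spent on helping the elderly in basic Activities of Daily Living and Instrumental Activities will be specified". It values that time by a replacement method that "assesses the time spent on informal care adjusted to market prices of a professional who has to do this work". The result enters one of three costing perspectives, the "social perspective (including all relevant costs: direct medical care + formal care (social services) and informal care".

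Annex 3 holds the forms. Each carer questionnaire has a daily table and a weekly table, once for the principal carer and once for other carers: Q19-Q22 at baseline, Q10-Q13 at week 12 and at week 52. The weekly question to the principal carer reads "How much time do you invest in a normal WEEK on each one of the following activities". The rows are:

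- Daily (6): hygiene and dressing or changing, bathing, feeding, moving indoors, cooking, drugs.
- Weekly (7): travel, contact with health care suppliers, home adaptations, shopping, finances and administration, social and leisure activities, supervision.

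Appendix 2 holds the scales for the first primary outcome, disability. Lawton item D is housekeeping, with a lowest category "Does not participate in any housekeeping tasks". Lawton item E is laundry, with a lowest category "All laundry must be done by others". Toilet use is a separate Barthel item, with a middle category "needs help, but can do something alone".

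**The concern.** Section 10 describes an informal care cost that covers help with both basic and instrumental activities. Two of the trial's own instrumental activities, housekeeping and laundry, have no place in the tables that feed that cost. A relative who does the patient's washing and cleaning has nowhere obvious to record it, so that work is priced at zero.

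Paid help is not limited in this way. The baseline questionnaire for the subject asks for weekly hours of a professional carer (Q5c) and days of home help (Q7), without restricting the tasks. The same housework can therefore be costed when a paid helper does it and not when a family member does. If the intervention shifts such work between family and services, the paid side enters the social-perspective cost and the family side does not.

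At stake are the level of informal care cost and, depending on how the arms differ, the cost difference in the social-perspective ICER.

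**Working it through.** The plan attaches no figure to this point, so there is nothing to reproduce. The check is a match of rows to items, followed by the algebra of an omitted component.

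**1. Rows against the trial's scales.**

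- Lawton: shopping, food preparation, transport, medication and finances each have a row. Telephone has none of its own, but the time could fall under health care contacts, finances or social activities. Housekeeping (D) and laundry (E) have no row.
- Barthel: feeding, bathing, grooming, dressing and mobility are covered. Transfers and stairs fit under moving indoors. Toilet use, bowels and bladder are not named, but the row "On basic hygiene and dressing or changing them" may take in some of that help.

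The last row label of the other-carers weekly table at week 52 is not legible in the text available. It is not counted as a gap.

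**2. Is there a fallback?** No carer table has a catch-all row, and no carer form asks for total hours of care. The subject's baseline form asks for hours only from a professional carer.

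**3. Effect on level and on difference.** Let L be listed and O omitted weekly hours, p the hourly price, a the intervention arm and b usual care, as in section 10's ICER.

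- Shortfall in level = O / (L + O).
- Recorded saving = L_b − L_a.
- True saving = (L_b − L_a) + (O_b − O_a).
- Recorded minus true value of (C_a − C_b) = −p × (O_a − O_b).

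The level is too low whenever O is above zero. The difference is wrong only when O differs between arms, and the sign of the error follows the sign of that difference.

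**4. Illustration.** All inputs here are assumed, because the documents give none: L = 20 h/week under usual care, a 10% fall in listed time under the intervention (recorded saving 0.10 × 20 = 2.0 h/week), and O = 2, 5 or 10 h/week under usual care.

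| O (h/week) | Shortfall in level | Recorded saving | True saving, O falls 10% | True saving, O unchanged | True saving, O rises 10% |
|---|---|---|---|---|---|
| 2 | 2/22 = 9.1% | 2.0 | 2.2 | 2.0 | 1.8 |
| 5 | 5/25 = 20.0% | 2.0 | 2.5 | 2.0 | 1.5 |
| 10 | 10/30 = 33.3% | 2.0 | 3.0 | 2.0 | 1.0 |

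A euro figure would also need p, which the documents do not give.

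**The case against.** **Section 10 does not promise one row per scale item.** It says only that time on the two classes of activity is specified, and the forms cover both classes. That is fair as far as it goes. But housework and laundry are whole tasks with no natural home in the 13 rows, and the social perspective is described as including all relevant costs.

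**Toilet and continence help is probably recorded.** A carer could enter it under hygiene and changing, or under moving indoors. This stands: it is unclear wording, not a demonstrated omission.

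**Both arms use the same forms, so the omission cancels.** This holds only if omitted time is equal in the two arms. A reader might infer the opposite, that any saving must be understated. The documents do not support that either. It follows if omitted time falls along with disability, which is what the trial hopes for, but the plan has no data on it, and step 3 shows that the error can be zero or reversed.

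**Lawton is repeated at 3 and 12 months, so the gap can be bounded.** This is partly right. Changes in housekeeping and laundry ability can inform a sensitivity analysis, but they are not hours. Housekeeping also scores 1 for a patient who needs help with every home maintenance task, so the item score can miss much of the help in question.

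**The scope is narrow.** This stands. Informal care enters one of three perspectives, carer forms exist only for patients with an informal carer, and cost-effectiveness is a secondary outcome.

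**Conclusion.** The concern holds for housework and laundry, for the missing other-help row, and as an ambiguity for toilet and continence care. The level of informal care cost in the social perspective is understated unless carers put this time under another row. Under the assumed 2 to 10 omitted hours beside 20 listed, the shortfall is 9% to 33%.

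The arm difference and the social-perspective ICER can be misstated, with a direction that depends on how omitted time responds to the intervention. The documents do not settle that direction and supply neither hours nor prices to size it. The clinical primary outcomes and the two narrower costing perspectives are not affected. The change is still worth making, because hours that no form asks for cannot be measured afterwards.

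**What to change.** In every carer table (Q19-Q22 at baseline, Q10-Q13 at week 12 and week 52), for principal and other carers:

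- add a row for housework and laundry;
- add one row for other help;
- name toilet and continence care, either in its own row or within the hygiene row.

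Compute the informal care cost in section 10 from the extended list.

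The cost is two or three more lines per table and a slightly longer interview. Carers interviewed before the change will lack the new rows, so the eCRF should record the form version, and a sensitivity analysis should compare results with and without the added rows.

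If the forms cannot change, section 10 should state that these tasks are excluded from informal care, and the social-perspective claim should be limited accordingly.

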4. WHAT IS YOUR MAIN WORKING SITUATION?

- I am employed
- I am unemployed
- Retired or pensioner ⇒ Skip to question #7
- Domestic tasks ⇒ Skip to question #8
- N/A ⇒ Skip to question #8

5. Have you had any work-related problem for caring the subject in the last 6 months?

- Yes
- No ⇒ Skip to question #8

6. In case of yes, please specify this

- I requested ____ days leave of absence
- I was working ____ hours less a day for ____ days
- I am working ____ hours less a day
- I do not work less hours a day but I have problems fulfilling my working hours
- I had to leave work because of illness the person I care
- Other problems: _____

7. Retirement (only to be answered in case the carer is retired or a pensioner)**e. Have you had to retire early to care for the subject?**

- Yes
- No ⇒ Skip to question #8

f. **In case of yes, please specify:**

- I retired early at the age of ____ years

SOCIAL, FAMILY AND LEISURE TIME- RELATED PROBLEMS

8. Have you had any family, social o leisure time-related problem for caring the subject in the last 6 months?

- Yes
- No ⇒ Skip to question #10

9. In case of YES, please specify this(multiple choice option):

- I had to reduce my leisure time
- I have conflicts with my partner or my family
- I have no time to see or visit my friends
- I have no time to take care of myself or other people
- I have failed to start a family / I have not been able to have children (or more children)

Regarding the role played by you as PRINCIPAL CARER...

10. How much time do you invest in a normal DAY for each one of the activities?

Please specify the approximate time you spend daily on each activity

On basic hygiene and dressing or changing them	hours	minutes	a day
On bathing or showering them	hours	minutes	a day

On feeding them	hours	minutes	a day
On helping them to move around within the house	hours	minutes	a day
On cooking and preparing meals	hours	minutes	a day
Administration of drugs	hours	minutes	a day

11. How much time do you invest in a normal WEEK on each one of the following activities?

Please specify the approximate time you spend weekly on each activity

On helping them to travel outside the house	hours	minutes	a week
On helping them to contact health care suppliers	hours	minutes	a week
On helping them to organise home adaptations	hours	minutes	a week
On shopping	hours	minutes	a week
On financial, administrative or legal affairs	hours	minutes	a week
On social and leisure activities	hours	minutes	a week
Monitoring and supervision (falls)	hours	minutes	a week

Regarding the role played by OTHER CARERS (e.g. the rest of the family)

12. How much time in a normal DAY do other carers spend on each one of the following activities?

Please specify the approximate time these people spend daily on each activity

On basic hygiene and dressing or changing them	hours	minutes	a day
On bathing or showering them	hours	minutes	a day
On feeding them	hours	minutes	a day
On helping them to move around within the house	hours	minutes	a day
On cooking and preparing meals	hours	minutes	a day
Administration of drugs	hours	minutes	a day

13. How much time do other carers spend in a normal WEEK on each of the following activities?

Please specify the approximate time these people spend weekly on each activity

On helping them to travel outside the house	hours	minutes	a week
On helping them to contact health care suppliers	hours	minutes	a week
On helping them to organise home adaptations	hours	minutes	a week
On shopping	hours	minutes	a week
On financial, administrative or legal affairs	hours	minutes	a week
On social and leisure activities	hours	minutes	a week

			
--	-------	--	--	--

